	
95% confidence intervals will be calculated. Statistical procedures to check on a normal distribution of data, to be applied in case of non-normally distributed data, and to verify and handle minimization factors will be described in the statistical analysis plan, which will be finalized prior to unblinding.
 
2. 28-day mortality (all cause death) The percentage of patients who have died at day 28 will be presented by treatment group. Patients who will be discharged from hospital or early terminated before Day 28 will be considered having an event on the day of discharge or early termination, if a telephone interview was not possible and/or no information about alive/death status is known. The Chi-squared or Fisher's exact test will be used to compare proportions. 95% CIs will be additionally calculated. Logistic regression analyses will be conducted considering additional co-factors (will be detailed in the statistical analysis plan).3. Ventilator-free days (VFD) up to 28 days or hospital discharge VFD will be analyzed for both all patients as well as for the subgroup of patients who were alive at day 28 or hospital discharge. For the analysis of all patients separate analyses will be conducted for patients who died: a) VFD will be set to 0, b) the observed VFD until death will be considered. Summary tables will be generated the VFD will be compared using Wilcoxon rank sum test. In addition, bootstrap methods will be applied to calculate 95% confidence intervals and two-sided p-values for the difference in means.4. Proportion of responders, defined as ≥ 2 improvement in WHO's 11-Point Score system at day 7, 10, 14 and 28 Similar analyses as for 28-day mortality will be conducted.5. Time to death (all cause) will be analyzed using Kaplan-Meier estimates and plots, log-rank test, and Cox proportional hazards model (adjusted for minimization factors to derive hazard ratios and corresponding 95% confidence intervals). Patients who will be alive at day 28, or who will be discharged from hospital before day 28 will be censored at discharge if they cannot be reached at or after day 28 by means of a telephone interview. Further details will be described in the statistical analysis plan.6. Proportion of patients with any use of invasive mechanical ventilation up to 28 days or hospital discharge. Similar analyses as for 28-day mortality will be conducted.7. Time to first use of invasive mechanical ventilation up to 28 days or hospital discharge. Similar analyses as for time to death will be conducted.8. Absolute values and absolute change in P/F ratio over time The PF ratio is defined as PaO₂ [mmHg] divided by FiO₂ [%] and will be evaluated on each visit. Summary statistics for the PF ratio for both the absolute values and the absolute change from Baseline (day 1) will be tabulated.9. Absolute values and absolute change in the modified Sequential organ failure assessment score (mSOFA score) over time Similar analyses as for the PF ratio will be conducted.

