8.3.3.1 Withdrawal of Patients from the Clinical Trial

The following circumstances may lead to discontinuation of the study by an individual patient who will then be recorded as a drop-out, include but are not limited to the following:

- Withdrawal for personal reasons
- AEs necessitating withdrawal from the clinical trial
- Occurrence of a severe adverse reaction (SAR)
- Sudden incidence of diseases
- Circumstances in which the health of the patient would be endangered upon continued participation in the clinical trial
- Lost to follow-up
- Other (must be specified)

If a patient withdraws from the study at any time either at his or her request or at the investigator's discretion, an "End-of-Study/Early Termination" visit should be performed and the "End of Study" eCRF section should be used to collect the relevant information. The visit may also be performed as a phone visit or in-home visit (in Russia). The reason(s) for withdrawal must be recorded on the relevant page of the patient's eCRF and the patient's source data. Patients discharged from hospital before day 28 will be contacted by telephone to assess if they are alive at day 28.

It is vital to obtain follow-up data for any patient withdrawn from the study because of an AE. Every effort must be made to undertake protocol-specific safety follow-up procedures. If a patient is discontinued due to an AE, the event should be followed up until resolution or until the event becomes chronic.

The Data Safety Monitoring Board may also recommend withdrawal of patients.

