8.7.1.2.4 Statistical Analysis

Continuous variables will be summarized with means, standard deviations, medians, lower and upper quartiles, minimums and maximums. Frequencies and percentages will be used to summarize categorical variables.

For time-to-event analyses censoring information will be used.

It is assumed that no patients will discontinue the study early prior to day 28 or hospital discharge in this Covid-19 setting. It is also assumed, that only very few missing values will arise due to not done evaluations. No imputation of missing values (e.g., no last observation carried forward (LOCF)) is planned, unless stated otherwise.

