3. Ventilator-free days (VFD) up to 28 days or hospital discharge

VFD will be analyzed for both all patients as well as for the subgroup of patients who were alive at Day 28 or hospital discharge. For the analysis of all patients separate analyses will be conducted for patients who died: a) VFD will be set to 0, b) the observed VFD until death will be considered. Summary tables will be generated the VFD will be compared using Wilcoxon rank sum test. In addition, bootstrap methods will be applied to calculate 95% confidence intervals and two-sided p-values for the difference in means.

4. Proportion of responders, defined as ≥ 2 improvement in WHO's 11-Point Score system at day 7, 10, 14 and 28

Similar analyses as for 28-day mortality will be conducted.

5. Time to death (all cause) will be analyzed using Kaplan-Meier estimates and plots, log-rank test, and Cox proportional hazards model (adjusted for minimization factors to derive hazard ratios and corresponding 95% confidence intervals). Patients who will be alive at Day 28, or who will be discharged from hospital before day 28 with no information on death until day 28, will be censored at discharge if they cannot be reached at or after day 28 by means of a telephone interview. Further details will be described in the statistical analysis plan.

6. Proportion of patients with any use of invasive mechanical ventilation up to 28 days or hospital discharge

Similar analyses as for 28-day mortality will be conducted.

7. Time to first use of invasive mechanical ventilation up to 28 days or hospital discharge
Similar analyses as for time to death will be conducted. Patients without invasive mechanical ventilation will be censored on the last day of evaluation. For patients who died the observed time to first use of invasive mechanical ventilation will be considered; if a patient who died did not receive any mechanical ventilation, the patient will be censored on time of death.

8. Absolute values and absolute change in P/F ratio over time

The PF ratio is defined as PaO₂ [mmHg] divided by FiO₂ in [%] and will be evaluated on each visit. Summary statistics for the PF ratio for both the absolute values and the absolute change from Baseline (day 1) will be tabulated.

9. Absolute values and absolute change in the modified Sequential organ failure assessment score (mSOFA score) over time

Similar analyses as for the PF ratio will be conducted.

10. Time to a 2-point decrease in WHO scoring scheme.

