Separate models will be calculated for Day 7, 10, 14 and 28.

The odds ratio along with its associated 95% confidence intervals will be reported.

Time to death (all causes)

Time to death [days] = Date of death - Date of randomization.

Patients who will be alive at Day 28, or who will be discharged from hospital/early terminated before Day 28 will be censored at discharge/early termination if they cannot be reached at or after Day 28 by means of a telephone interview. Patients who will be reached at or after Day 28 by means of a telephone interview will be censored at the date of telephone contact if they are alive.

The following cases may occur:

- Patient discharged from hospital **and** discontinued before Day 28, will be followed up by telephone interview to check whether they are alive or dead, if unclear as no telephone interview available, death is assumed (worst case) at last available date of early termination, hospitalization or hospital discharge
- No discharge from hospital, **but** early discontinuation before Day 28 will be followed up by telephone interview to check whether they are alive or dead, if unclear as no telephone interview available, death is assumed (worst case) at date of early termination
- Discharged from hospital, **but** no discontinuation before Day 28: No telephone interview, but regular entry at Day 28 about alive/death status

Time to death (all causes) will be analyzed using Kaplan-Meier estimates and plots, log-rank test, and Cox proportional hazards model (adjusted for center and age to derive hazard ratios and corresponding 95% confidence intervals).

Kaplan-Meier estimates and Log-rank test

Kaplan-Meier table (product-limit “survival” estimates with 95%-CI, Standard error, Number of patient with event, Number of patient at risk) for Time to death [days], Kaplan-Meier Summaries of Event/Censoring (Number of patient with event, Number of patient censored, Total number of patients), Quartile Estimates (Median Time to Event, 1st Quartile, 3rd Quartile, 95%-CI) and Kaplan-Meier table (“survival” estimates with 95%-CI) for Timepoint (28 days). Time to death [days] will be displayed by a Kaplan-Meier-curve. Treatments groups will be compared with Log-rank test.

Cox proportional hazards model

The hazards ratio along with its associated 95% confidence intervals as well as parameter estimate and p-value (two-sided) will be reported.

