Page # of #

<Subtitle for description of contents - if applicable>

<Analysis set>

The numbering NNN of the tables/listings/graphs will be stated in the detailed description (Appendix A).

Following footnote will be used for all generated tables, listings, and graphs:

Date: <Actual date(ddmmmyyyy)>

Program: <Name of program>

All tables, listings, and graphs will be generated in A4 paper format.

The statistical evaluation will be performed using SAS version 9.4 or higher.

5 Changes from Protocol

In the following any changes on statistical aspects as described in the protocol are given:

- Wording of WHO's Proposed Core Outcome Measure Set for Clinical Studies of COVID-19 Infection for consistence (secondary endpoint):
 - Protocol: Time to a 2-point decrease in WHO scoring schema
 - SAP: Time to a to a 2-point decrease in WHO's 11-Point Score system
- Covariables used in statistical models and dynamic randomization
 - Protocol: Age as continuous variable
 - SAP: Age as dichotomous variable (<65 years vs. >= 65 years)

6 Signatures

Statistician:	
[name] FGK Clinical Research GmbH [name] [name] Germany	
11 Jan 2021 Date (ddmmmyyyy)	SN [Signature] Signature

Sponsor:	
[name] APEIRON Biologics AG [name]	
11 Jan 2021 Date (ddmmmyyyy)	[Signature] Signature

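### Time to death both censors and counts as dead the same patients of unknown status; Kaplan-Meier for time to discharge censors deaths, so it does not estimate the probability of discharge

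*SAP*

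**What the plan says.** **Time to death.** SAP section 4.4.2 first states that patients discharged or terminated early before Day 28 "will be censored at discharge/early termination if they cannot be reached at or after Day 28 by means of a telephone interview". Three cases follow:

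- Discharged and discontinued before Day 28: "if unclear as no telephone interview available, death is assumed (worst case) at last available date of early termination, hospitalization or hospital discharge".
- Not discharged but discontinued before Day 28: "if unclear as no telephone interview available, death is assumed (worst case) at date of early termination".
- Discharged but still in the study: no telephone interview, because vital status comes from the regular Day 28 entry.

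The protocol only censors for this endpoint, and it addresses discharged patients only. Section 8.7.1.2.5 says that those "with no information on death until day 28, will be censored at discharge if they cannot be reached" are handled this way; the synopsis says that patients who "will be discharged from hospital before day 28 will be censored at discharge if they cannot be reached at or after day 28" are. Neither mentions early termination without discharge. The protocol reserves the worst-case rule (unknown counts as an event) for the primary endpoint and 28-day mortality.

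SAP section 4.7 rules out any imputation of missing values. SAP section 5 opens with "In the following any changes on statistical aspects as described in the protocol are given" and then lists only the wording of the WHO scale endpoint and the coding of age.

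**Time to hospital discharge.** Protocol section 8.7.1.2.5 and SAP section 4.4.2 both censor patients who die on the day of death. The SAP then plans a Kaplan-Meier table and curve, quartiles, a 28-day estimate, a log-rank test and a Cox model. Its body names no competing-risk method. SAP section 4.1 separately tabulates the percentage discharged by visit.

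**The concern.** A patient cannot be both censored and an event on the same date. If the assumed-death cases prevail, the censoring clause has almost nobody left to apply to, because discharged patients who stay in the study have a Day 28 entry. The case list repeats the one given for 28-day mortality, which suggests that it was carried across without being reconciled with the censoring sentence. At stake are the mortality curve, its 28-day value, the hazard ratio and the log-rank test, with the choice left to whoever programs the analysis.

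For discharge the issue is the quantity estimated, not a contradiction. A patient who has died can no longer be discharged. Censoring at death treats that patient as if discharge could still happen at the rate seen in the survivors. The resulting curve would naturally be read as the chance of having left hospital, which it is not.

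**Working it through.** **The plan's own figure.** Neither document gives a figure for these two endpoints. The primary sample size reproduces: [1.960 × √(2 × 0.4 × 0.6) + 0.842 × √(0.5 × 0.5 + 0.3 × 0.7)]² / 0.2² = 93 per group. It does not depend on this point.

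**Time to death: 28-day value.** Assumptions (the documents give no rates): 100 patients per arm, 15 known deaths evenly spaced over days 2 to 26, patients of unknown status leaving at day 10.5, all others followed to day 28. Five deaths fall before day 10.5 and ten after it.

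- 5 unknown, censored: survival = 0.95 × (80/90) = 0.844, so mortality is 15.6%.
- 5 unknown, assumed dead: 20/100 = 20%.
- 2 unknown: 1 − 0.95 × (83/93) = 15.2% against 17%.
- 8 unknown: 1 − 0.95 × (77/87) = 15.9% against 23%.

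**Time to death: hazard ratio (Cox, Efron ties) and log-rank p.** Same set-up, varying known deaths and unknowns per arm:

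| Known deaths | Unknown | Censored | Assumed dead |
|---|---|---|---|
| 15 v 15 | 5 v 5 | 1.00 | 1.00 |
| 15 v 15 | 2 v 8 | 1.05 (p 0.90) | 1.41 (p 0.285) |
| 10 v 20 | 2 v 2 | 0.47 (p 0.048) | 0.52 (p 0.062) |
| 10 v 20 | 5 v 5 | 0.47 (p 0.047) | 0.57 (p 0.080) |

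The rule therefore matters when unknowns are unequal between arms. It also matters when they are equal but known deaths differ, because the same number of assumed deaths added to each arm pulls the ratio towards 1.

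**Time to discharge.** Assume 70% discharged and 15% dead by day 28, with constant hazards.

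- Total hazard = −ln(1 − 0.70 − 0.15)/28 = 0.06775 per day.
- Discharge hazard = 0.06775 × 0.70/0.85 = 0.0558 per day.
- One minus Kaplan-Meier at day 28 = 1 − exp(−28 × 0.0558) = 79.0%, against 70% actually discharged. A simulation of 200,000 patients gave 78.9%.
- Kaplan-Meier median = ln 2/0.0558 = day 12.4. The true median is −ln(1 − 0.5 × 0.85/0.70)/0.06775 = day 13.8.
- Kaplan-Meier third quartile = ln 4/0.0558 = day 24.8, although fewer than 75% are discharged by day 28.

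With 70% discharged, the excess at day 28 is 2.6, 5.5, 9.0 and 13.3 percentage points for 5%, 10%, 15% and 20% deaths.

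Timing also matters. Keeping 70% and 15% but spreading events evenly:

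- deaths over days 1 to 7, discharges over days 4 to 20: 82%;
- deaths over days 14 to 28, same discharges: 72%;
- deaths over days 21 to 28, after the last discharge: exactly 70%.

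Inflation therefore needs discharges that come after deaths.

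**The case against.** **Unknown status may not occur.** The protocol states "It is assumed that no patients will discontinue the study early prior to day 28 or hospital discharge in this Covid-19 setting" and also that "Patients discharged from hospital before day 28 will be contacted by telephone to assess if they are alive at day 28". If that holds, the two time-to-death rules give identical results. This stands as a limit on size. It does not settle which rule applies, and the SAP wrote out both because it foresaw the case.

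**Balance between arms might seem to make the choice harmless.** A reader could infer this from blinding and randomization. The 10 v 20 rows above show otherwise: with five unknown in each arm the nominal p moves from 0.047 to 0.080.

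**The no-imputation statement might seem to settle it.** SAP section 4.7 favours censoring, but the same SAP uses the worst case for the primary endpoint and 28-day mortality, so section 4.7 cannot be decisive here.

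**Protocol and SAP agree on discharge.** They do, so there is no contradiction in that part, and log-rank and Cox with deaths censored are valid for the cause-specific hazard of discharge. A reader might go further and call those tests invalid, or say that Kaplan-Meier is always too high. Neither is right. Agreement does not, however, turn one minus Kaplan-Meier into a probability of discharge.

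**Appendix A was not supplied.** Titles and footnotes there might label the outputs or explain the difference from the crude percentages in SAP section 4.1. Only the SAP body can be said to lack a label.

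**Conclusion.** Both parts hold, and both should be fixed.

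- **Time to death:** two incompatible rules cover the same patients, namely those who discontinued before Day 28 with vital status unknown. The supplied text gives no precedence and SAP section 5 declares no departure. Under the assumptions above, 28-day mortality differs by about 2 points with 2 unknown per 100 and by 4.4 points (15.6% v 20%) with 5. The difference is nil if no status is unknown.
- **Time to discharge:** the curve, quartiles and 28-day value are not probabilities of discharge. They are too high when discharges follow deaths: 79% against 70% in the constant-hazard example with 15% deaths, and 70% to 82% across the timings tried. All rates are assumed.

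A reader might infer that the primary endpoint or 28-day mortality is compromised. The documents do not support that: both apply the worst case consistently in protocol and SAP. The two endpoints here are secondary, and the protocol describes the secondary tests as exploratory.

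**What to change.** Settle the following before unblinding.

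- **Time to death:** keep the protocol's censoring rule as the main analysis. Remove the two assumed-death cases from this endpoint, state that censoring also covers early termination without discharge, and run the worst case as a labelled sensitivity analysis. Add a footnote that 28-day mortality uses the worst case, so the death counts may differ. Alternatively, make the worst case the main analysis, delete the censoring clause and list the departure in SAP section 5. Either is workable; leaving both is not.
- **Time to hospital discharge:** report Aalen-Johansen cumulative incidence with death as a competing event. Take the quartiles (not reached, where that applies) and the 28-day value from it. Keeping deaths in the risk set as not discharged through Day 28 would also serve. Label the log-rank and Cox results as cause-specific.
- **Related endpoints:** the protocol also censors deaths for time to first invasive ventilation and time to a 2-point WHO decrease, and the SAP plans the same Kaplan-Meier outputs for them. Check both for the same point.

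The cost is SAP wording, possibly one entry in section 5, and small program changes. No new data are needed.

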4.4.1 Analysis of Primary Efficacy Endpoint

The primary endpoint is a composite endpoint of all cause-death or invasive mechanical ventilation (up to 28 days or hospital discharge).

The following null hypothesis will be tested:

- $H_0: p_{APN01} = p_{Placebo}$

versus the alternative

- $H_1: p_{APN01} \neq p_{Placebo}$

H_0 will be tested using a Chi-squared test. The level of significance is 5% (two-sided). In addition, logistic regression analyses will be conducted considering additional co-factors.

All cause-death

The percentage of patients who have died at Day 28 will be presented by treatment group.

Patients with death from any cause will be used for this endpoint as part of responder. Patients who are still alive at Day 28 will be considered as non-event.

The following cases may occur:

- Patient discharged from hospital **and** discontinued before Day 28, will be followed up by telephone interview to check whether they are alive or dead, if unclear as no telephone interview available, death is assumed (worst case) at last available date of early termination, hospitalization or hospital discharge
- No discharge from hospital, **but** early discontinuation before Day 28 will be followed up by telephone interview to check whether they are alive or dead, if unclear as no telephone interview available, death is assumed (worst case) at date of early termination
- Discharged from hospital, **but** no discontinuation before Day 28: No telephone interview, but regular entry at Day 28 about alive/death status

Invasive mechanical ventilation (up to 28 days or hospital discharge)

Invasive mechanical ventilation is defined as patients who are intubated or have a tracheostomy tube and are receiving positive pressure ventilation. Patients with at least one invasive mechanical ventilation (event with type of ventilation 'Mechanical ventilation') up to 28 days or hospital discharge will be used for this endpoint as part of responder.

Chi-squared test

Proportion of responder, i.e. those patients that died or having an invasive mechanical ventilation (up to 28 days or hospital discharge), as well as the p-value (two-sided) will be reported.

Logistic regression

A logistic regression with the responder (yes/no) as independent variable will be applied.

The following co-factors will be included in the logistic regression:

- Arterial hypertension

- ❑ Diabetes
- ❑ Coronary artery disease
- ❑ Age (<65 years vs. >=65 years)
- ❑ Center

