Proportion of patients with any use of invasive mechanical ventilation (up to 28 days or hospital discharge)

Requirement and type of ventilation will be presented using frequency tables.

Chi-squared test or Fisher’s exact test

Proportion of responder, i.e. those patients that having an invasive mechanical ventilation (up to 28 days or hospital discharge), as well as the p-value (two-sided) will be reported.

Logistic regression

The following co-factors will be included in the logistic regression:

- Arterial hypertension
- Diabetes
- Coronary artery disease
- Age (<65 years vs. >=65 years)
- Center

The odds ratio along with its associated 95% confidence intervals will be reported.

Time to first use of invasive mechanical ventilation (up to 28 days or hospital discharge)

Time to first use of invasive mechanical ventilation [days] = Start date of first ventilation - Date of randomization.

If ventilation started before randomization, the time to first use will be set to 0 (minimal possible duration).

Patients without documented invasive mechanical ventilation who completed the study or was early terminated or discharged from hospital before Day 28 will be censored at the date of study completion, discontinuation or discharge from hospital respectively.

Time to first use of invasive mechanical ventilation (up to 28 days or hospital discharge) will be analyzed using Kaplan-Meier estimates and plots, log-rank test, and Cox proportional hazards model (adjusted for center and age to derive hazard ratios and corresponding 95% confidence intervals).

Kaplan-Meier estimates and Log-rank test

Kaplan-Meier table (product-limit “survival” estimates with 95%-CI, Standard error, Number of patient with event, Number of patient at risk) for Time to first use of invasive mechanical ventilation [days], Kaplan-Meier Summaries of Event/Censoring (Number of patient with event, Number of patient censored, Total number of patients), Quartile Estimates (Median Time to Event, 1st Quartile, 3rd Quartile, 95%-CI) and Kaplan-Meier table (“survival” estimates with 95%-CI) for Timepoint (28 days). Time to first use of invasive mechanical ventilation [days] will be displayed by a Kaplan-Meier-curve. Treatments groups will be compared with Log-rank test.

Cox proportional hazards model

The hazards ratio along with its associated 95% confidence intervals as well as parameter estimate and p-value (two-sided) will be reported.

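### The SAP leaves "invasive" out of the event date for time to first invasive ventilation and scores ventilation begun before randomisation as time 0; the primary composite's ventilation component has no start point

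*SAP*

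**What the plan says.** **Time to first use (SAP 4.4.2).** The event time is defined as "Time to first use of invasive mechanical ventilation [days] = Start date of first ventilation - Date of randomization". The next rule reads "If ventilation started before randomization, the time to first use will be set to 0 (minimal possible duration"). The censoring rule then covers "Patients without documented invasive mechanical ventilation who completed the study or was early terminated" or were discharged before Day 28. So the title and the censoring rule specify invasive ventilation, while the event date and the time-0 rule do not.

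**Types of ventilation.** For the proportion endpoint just before it, the SAP states "Requirement and type of ventilation will be presented using frequency tables", which implies that more than one type is recorded.

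**Protocol 8.7.1.2.5, secondary endpoint 7.** "For patients who died the observed time to first use of invasive mechanical ventilation will be considered". The protocol has no time-0 rule.

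**SAP section 5.** It opens with "In the following any changes on statistical aspects as described in the protocol are given" and lists two items: wording of the WHO score, and age as a dichotomous variable. Neither concerns this endpoint.

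**Primary composite (SAP 4.4.1).** The ventilation component is restricted by type: "Patients with at least one invasive mechanical ventilation (event with type of ventilation", where the required entry is 'Mechanical ventilation'. On the period covered, the same sentence says only "up to 28 days or hospital discharge will be used for this endpoint as part of responder". A type filter and an upper limit are given, but no start point. Protocol 8.7.1.2.5 supplies none either, and the proportion endpoint in SAP 4.4.2 has the same gap.

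**The concern.** A programmer who follows the formula as written would take the earliest ventilation record of a patient who has an invasive event. If that record is non-invasive support, the event is real but its date is wrong, and it is exactly 0 if the support began before randomisation. If the formula is instead taken to mean invasive ventilation, the time-0 rule turns a state present before randomisation into a new event, in a patient who was never at risk of a first use.

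At stake for this endpoint are the Kaplan-Meier curve, its quartiles and, in some circumstances, the power of the log-rank test.

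For the primary composite, a patient already on invasive ventilation at randomisation counts as an event in either arm whatever the treatment does. That dilutes the difference. The SAP does foresee ventilation begun before randomisation, both here and in its rule for ventilator-free days. No criterion in protocol 8.3.1 or 8.3.2 expressly excludes a patient intubated for COVID-19. The only mention of a ventilator is dependency, listed under severe chronic pulmonary disease.

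**Working it through.** **1. What the rules do to each type of patient**

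| Patient | Formula taken literally | Formula read as invasive |
|---|---|---|
| Non-invasive support only | Censored by the censoring rule | Censored |
| Non-invasive support at entry, intubated later | Event at time 0 | Event at the true date |
| Non-invasive support begun after randomisation, intubated later | Event dated from the non-invasive start | Event at the true date |
| Intubated before randomisation | Event at time 0 | Event at time 0 |

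Example: non-invasive support from Day -1, randomised on Day 1, intubated on Day 6. The time is 0 as written, and 6 − 1 = 5 days from the invasive episode.

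**2. Effect on the time-to-event analysis (simulation; every input is an assumption)**

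There are 100 patients per arm and 4,000 trials per case. Days to intubation are exponential, rounded up and capped at 27, with mean 6 (4 vs 9 in the delay case). Patients without an event are censored uniformly on Days 5 to 28. A random 10%, 25% or 50% of events is moved to time 0, and the log-rank test is two-sided at 0.05.

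| Case (placebo vs APN01 intubated) | Correct dates | 10% | 25% | 50% |
|---|---|---|---|---|
| Prevention only, 40% vs 22% | 78.4% | 78.1% | 78.6% | 79.0% |
| Prevention plus delay, 40% vs 27% | 64.3% | 61.4% | 58.5% | 54.3% |
| No effect, 40% vs 40% | 5.3% | 5.3% to 5.4% across the three shares | | |

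The false step at time 0 in the placebo curve is 0.40 × 10%, 25% or 50% = 4, 10 or 20 points. With mean 6 days, the placebo Kaplan-Meier first quartile is typically Day 6 with correct dates. It is still Day 6 at 10%, then about Day 4 to 5 at 25% and Day 2 at 50%. A repeat with 2,000 trials per case agreed within simulation error. Only shifts to time 0 were modelled, not mis-dating after randomisation.

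**3. Primary composite**

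Inputs from protocol 8.7.2: 50% vs 30%, two-sided 0.05, 93 per group for 80% power, 100 per group enrolled, chi-squared test.

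Power = Φ{[|p₁ − p₂|√n − 1.96√(2p̄(1 − p̄))] / √(p₁(1 − p₁) + p₂(1 − p₂))}, with p̄ the mean of p₁ and p₂.

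Plan's own figure, n = 93: (0.2 × 9.644 − 1.96 × 0.6928) / 0.6782 = 0.842, and Φ = 80.0%. It reproduces. At n = 100 the power is 82.8%.

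Now let a share f of each arm be on invasive ventilation at randomisation and score as events. The rates become f + (1 − f) × 0.5 and f + (1 − f) × 0.3. The last column leaves these patients out: 50% vs 30% with 100(1 − f) per arm.

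| f (assumed) | Rates | Power, 100 per arm | Power, 93 per arm | Left out, from 100 per arm |
|---|---|---|---|---|
| 0 | 50.0% vs 30.0% | 82.8% | 80.0% | 82.8% |
| 1% | 50.5% vs 30.7% | 81.9% | 79.0% | 82.4% |
| 2% | 51.0% vs 31.4% | 80.9% | 78.0% | 82.0% |
| 5% | 52.5% vs 33.5% | 77.9% | 74.8% | 80.8% |

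At 100 per arm, power drops below 80% once f exceeds 2.9%.

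**The case against.** The ordinary reading of the formula is shorthand. Its left-hand side says invasive, as do the title and the censoring rule, and SAP 4.4.1 supplies the type filter. A reader might infer that the SAP dates the event from the first ventilation of any type. It does not say so: it names no type. Appendix A and the eCRF, which might settle the matter, are not available. This stands, and the point is therefore an omission that conflicts with its surroundings, not a rule to use any type. The shorthand reading still does not rescue the time-0 rule, which then turns intubation before randomisation into a new event.

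The endpoint is exploratory: protocol 8.7.1.2.5 says secondary variables are tested descriptively. The power loss appears only in the delay case, under invented shares. This also stands and limits the weight of the point.

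Intubation at entry is probably rare. Protocol 4.3 has every participant sign consent, and inclusion criterion 3 describes room air or supplemental oxygen. The SAP's provisions for ventilation begun before randomisation fit non-invasive support equally well, so they do not show that intubated patients were expected. This is right for the primary composite, where the effect is probably small.

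**Conclusion.** The point holds as an internal inconsistency that is cheap to remove. The event date and the time-0 rule conflict with the endpoint's own title and censoring rule and with protocol 8.7.1.2.5. SAP section 5 declares no such change, so the wording looks unintended. Neither reading gives a sound result for every patient.

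The size is modest. Type I error is not affected. The Kaplan-Meier curve can show a false step at time 0, and its first quartile moves only when the share of mis-dated events is substantial. Log-rank power changes only if treatment delays intubation as well as preventing it. All of this rests on assumed shares, rates and times, because the documents give none.

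For the primary composite, a reader might infer that the analysis is biased or the trial underpowered. The documents do not support that. Cases present at entry fall in both arms by randomisation and dilute the difference without inflating error, and at 100 per arm the power stays above 80% up to a share of about 2.9%. The missing start point calls for a sensitivity analysis, not a new primary definition.

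**What to change.** Before unblinding:

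- **Time to first use (SAP 4.4.2).** Date the event from the first ventilation record of type 'Mechanical ventilation', the filter already used in SAP 4.4.1, that starts after randomisation. Replace the time-0 rule by leaving out patients on invasive ventilation at randomisation, who are not at risk of a first use. The exclusion rests on a state present before randomisation, so it does not disturb the comparison. Because the formula works in dates, say how a start on the day of randomisation is treated.
- **Primary composite (SAP 4.4.1) and proportion ventilated (SAP 4.4.2).** Keep the definitions. Add one sensitivity analysis of both that excludes patients on invasive ventilation at randomisation. Identify them from the ventilation start dates, supported by a pre-dose WHO score of 7 to 9 (protocol Annex 1).

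The cost is a few words, one sensitivity analysis and a slightly smaller set for the time-to-event analysis. All the data are already collected. If unblinding has taken place, the report should state which ventilation type and date were used and show both versions.
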